13.3 Enrollment and Study Duration

We expect to enroll at an average rate of two patients per month and complete accrual within two years. Patients will be followed for a minimum of one additional year. Thus study duration is expected to be approximately three years.

13.4 Statistical Analyses

Baseline characteristics will be summarized using descriptive statistics: count, percentage, range, median, mean, and standard deviation as appropriate. Data include demographics (age, sex, race/ethnicity), performance status, laboratory parameters and prior therapy.

Treatment duration will be summarized by the number of immunotherapy cycles (6 weeks each). Frequency and reason for dose modifications and discontinuation of any therapy will be detailed.

We will report the objective response rate with corresponding two-side 90% confidence interval (CI) using the exact binomial method (Armitage et al, 2002). We will also report the objective response rate, the median and range for time to response, and duration of CR or PR. Time to progression will be summarized by the median and range for patients whose best response is SD as well as for all patients who develop progressive disease.

The Kaplan-Meier method will be used to estimate progression-free and overall survival. Point estimates for the proportion of progression-free and surviving patients will be given for selected times, specifically 6 and 12 months, along with corresponding 95% confidence intervals using the log-log transformed method and Greenwood's variance. To the extent possible with 30-60 study patients, we will investigate the relationship between tissue and serum biomarkers and overall response using logistic regression. Similarly, biomarker associations with progression free and overall survival will be explored using the log rank test and Cox regression.

Safety will be assessed by tabulating toxicities according to type, grade, duration, and attribution to study treatment in accordance with *NCI Common Terminology Criteria for Adverse Events* (CTCAE version 4.0). We will also report the distribution of worst grade toxicity in study patients.

TTFields compliance data is collect during monthly in-home visits by Novocure representative in order to assess NovoTTF200A (OptuneTM) function and address patient concerns. The compliance rates are an average (mean \pm stdev) over the 28-31 days of the month and provided in graphical and numerical form. Appendix D shows sample compliance reports with weighted average (mean \pm stdev) per month. These data are provided as part of standard of care and included in the patient medical record. The weighted average will be compared to ORR, OS and PFS using the appropriate logistic or Cox regression models.

Quality of life will be assessed using the NRG/RTOG tool Functional Assessment of Cancer

Therapy-Brain (FACT-Br). FACT-Br is a validated tool measuring general quality of life (QOL) that assesses symptoms or problems associated with CNS tumors across 5 scales (Cella DF, 1993; Weitzner MA, 1995). FACT-Br yields data about total QOL, as well as dimensions of disease specific physical, social/family, emotional, and functional well-being. The FACT-Br is written at the 4th grade reading level. Patients can complete it in 5-10 minutes. The self-report of quality of life can be completed by the patient or with the assistance of the examiner and does not require pre-certification.

Analysis of QOL will focus on the 33-item FACT-G score and the 20-item brain subscale, FACT-BR. Scores will be calculated in accordance with FACIT scoring guidelines (www.facit.org). Descriptive summaries of FACT-G and FACT-BR at baseline and at each planned follow-up will include median and range, means and standard deviations as well as graphical depiction. To the extent that a clinically meaningful difference can be established, we will also categorize changes from baseline as indicating improvement, worsening, or no change and summarize these by counts and percentages.

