13. STATISTICAL CONSIDERATIONS

13.1 Study Design and Sample Size

We propose an open label, two parallel arm, two-stage, phase II trial to determine the efficacy, in terms of objective response rate (ORR), of combination therapy with tumor treating fields (TTFields) therapy, nivolumab with or without ipilimumab in adult patients with bevacizumabnaïve, recurrent glioblastoma. Best objective response rate (ORR) is defined as the proportion of evaluable patients who achieve complete (CR) or partial response (PR) according to modified immunotherapy iRANO criteria. Secondary objectives include safety, ORR by standard RANO criteria, overall survival (OS), progression-free survival (PFS), clinical benefit (defined as ORR plus stable disease >12 weeks), compliance rates of TTFields therapy at or above goal of 75%, and exploratory correlations between response or survival and compliance rates, serum and/or tumor tissue biomarkers. Primary analyses are performed for each arm, but secondarily assessed for the entire cohort as well.

The EF-11 study showed a response rate of 14% among patients with recurrent glioblastomas treated with TTFields alone compared to physician's choice medical therapy (Stupp et al, Eur J Cancer 2012). Thus, the null H0 is set at 14% and H1 (target ORR) set at 35% for each arm. Power is set at 85% with a 1-sided alpha of 0.05.

If no response is seen after 15 eligible patients are accrued in either arm, that arm will close for futility. Based on a MiniMax design, if >2 responses are seen on the first 15 patients in either arm, then 15 more patients will be accrued in the arm. If \geq 7 responses are seen among the 30 patients in either arm, this regimen deserves further investigation. Sample size will be 30 maximum per cohort/arm for a total of 30 to 60 subjects enrolled on study.

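### The 90% interval for ORR in 13.4 is built for a fixed sample, so it is not exact under the two-stage design and at 4/30 or 5/30 excludes a 35% target that a two-stage interval keeps

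*Combined protocol and SAP*

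**What the plan says.** Section 13.1 sets up a two-stage minimax design in each arm: "the null H0 is set at 14% and H1 (target ORR) set at 35% for each arm", and "Power is set at 85% with a 1-sided alpha of 0.05". The continuation rule is "if >2 responses are seen on the first 15 patients in either arm, then 15 more patients will be accrued in the arm", with "Sample size will be 30 maximum per cohort/arm". An arm is called worth pursuing if at least "7 responses are seen among the 30 patients in either arm".

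The sentence just before the continuation rule gives a different stopping rule: "If no response is seen after 15 eligible patients are accrued in either arm, that arm will close for futility". Section 13.5 puts the chance of stopping early under the null at 65%.

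For the analysis, 13.4 reports the ORR with a "two-side 90% confidence interval (CI) using the exact binomial method". Section 13.1 defines ORR as the simple proportion of responders among evaluable patients. Neither section adjusts the interval or the estimate for the stage 1 stop.

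**The concern.** The exact binomial (Clopper-Pearson) interval is exact when the sample size is fixed in advance. Here an arm reaches 30 patients only if it had at least 3 responses in its first 15. That condition changes which results count as being as low as, or lower than, the one observed, so the stated error per side no longer holds.

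In an uncontrolled phase II trial, the ORR and its interval are the main efficacy report. When an arm misses its cut-off, a reader will use the interval to ask whether the 35% target is still plausible. That is where the fixed-sample and two-stage intervals differ.

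**Working it through.** **Inputs.** From 13.1: p0 = 0.14, p1 = 0.35, n1 = 15, n = 30, continue if more than 2 responses. From 13.5: 65% early stopping under the null. From 13.4: 90% two-sided interval, so 5% per side. Below, X1 is the number of responses in the first 15 patients and S the total in 30.

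**1. Which stage 1 rule gives 65%?** With X1 ~ Bin(15, 0.14):
- Stop at 2 or fewer: 0.1041 + 0.2542 + 0.2897 = 0.648, which is the plan's 65%.
- Stop at zero only: 0.86^15 = 0.104.

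Only the first rule matches, so it is used from here on.

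**2. Does 5/30 exclude 35%?** A 90% interval excludes 35% from above if the lower-tail probability at 0.35 is below 0.05.
- Fixed sample: P(Bin(30, 0.35) ≤ 5) = 0.023, so 35% is excluded.
- Two-stage, with stagewise ordering (every arm stopped at stage 1 ranks below every arm that continued): P(X1 ≤ 2) + P(X1 ≥ 3 and S ≤ 5) = 0.0617 + 0.0097 = 0.071, so 35% is kept.

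The stopping term alone, 0.0617, already exceeds 0.05. Under this ordering no continuing arm can exclude 35% from above.

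**3. Intervals by outcome.** For arms stopped at 0, 1 or 2 of 15 the two methods give the same interval. For continuing arms:

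| Result | Planned 90% | Two-stage 90% (stagewise) |
|---|---|---|
| 3/30 | 2.8%-23.9% | 5.7%-36.4% |
| 4/30 | 4.7%-28.0% | 6.5%-36.5% |
| 5/30 | 6.8%-31.9% | 8.0%-37.1% |
| 6/30 | 9.1%-35.7% | 9.8%-38.5% |
| 7/30 | 11.5%-39.4% | 11.9%-40.8% |
| 8/30 | 14.0%-43.0% | 14.3%-43.6% |

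At 4/30 and 5/30 the stagewise, MLE and UMVUE orderings give the same two-stage interval. At 3/30 the answer depends on the ordering: the MLE ordering gives an upper limit of 28.1%, which also excludes 35%. At 6/30 both methods include 35%.

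**4. Coverage.** Summing exact probabilities over all two-stage outcomes, coverage of the planned interval is 95.5% at a true 14%, 93.9% at 20%, 94.6% at 35% and 89.3% at 40%. The minimum is near 36.4%. There the planned upper limit falls below the true rate for all arms stopped at stage 1 (probability about 0.050) and for 3 to 6 of 30 (about 0.025). The upper-side error is therefore 0.074. The lower-side error is 0.043, so coverage is 1 − 0.074 − 0.043 = 0.883. The stagewise interval keeps coverage at or above 90%.

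**5. Error at exactly 35%.** The planned interval lies wholly below 35% after 0 or 1 of 15 (0.0142) or 3 to 5 of 30 (0.0097), in total 0.024. The stagewise interval does so with probability 0.014. Both are under 0.05.

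**6. How often the two methods disagree about 35%.** A continuing arm ends at 3 to 5 of 30 with probability 17% at a true 14% and 1.0% at a true 35%.

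**7. The point estimate.** Averaged over all outcomes, the raw proportion is biased by −1.8 points at a true 14%, −2.0 at 20% and −0.7 at 35%. The UMVUE removes this average bias, but not among arms that continue. At a true 14% the raw proportion averages 19.0% in those arms and the UMVUE 24.0%. Root-mean-square error over all outcomes at 14% is 7.3 points for the raw proportion and 8.5 for the UMVUE.

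**8. If the zero-response rule governed instead.** At 5/30 the upper limits would be 31.9% (planned) and 32.0% (two-stage). The planned interval's minimum coverage would be 90.1%, and the point would disappear in practice.

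**The case against.** The strongest reply is that the planned interval does little harm. Its coverage is above 90% at most true rates, and the lowest value is 88.3%. Section 13.1 decides by response count, not by the interval, so 4/30 or 5/30 fails either way. At or above the cut-off the difference is at most about 1.4 points in the upper limit (7/30: 39.4% against 40.8%). All of this stands, and it is why the point is a cheap improvement and not a flaw in the trial's decision rule.

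Two stronger readings are tempting, and the plan's own figures support neither.

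- A reader might infer that the planned interval wrongly rules out the 35% target too often. It does not: at a true 35% this happens 2.4% of the time, within the 5% allowed. The excess error lies at true rates just above 35%. The disagreement at 4/30 and 5/30 concerns how those results should be read under this design.
- A reader might infer that the raw proportion should give way to the UMVUE, above all for arms that continue. Near the null that would make matters worse: in continuing arms the raw proportion is already too high on average and the UMVUE is higher still. At 5/30 it would report 22.5% in place of 16.7%.

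A further objection is that the stage 1 rule is unsettled, since 13.1 contains two rules and 13.5 says only that stopping will be considered. This also stands. The 65% figure identifies the intended rule but does not replace a clear statement of it.

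**Conclusion.** The point holds as a minor one about the interval. Under the rule that reproduces the plan's 65%, the interval in 13.4 is not exact. Coverage drops to 88.3% at worst, with 7.4% upper-side error against 5%, and at 4/30 and 5/30 the planned interval excludes a target that the two-stage interval retains. The raw proportion can stay as the reported estimate.

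This rests on three assumptions: the stage 1 rule is stop at 2 or fewer of 15, the rule is followed when it is met, and the stages are 15 and 15 evaluable patients. The 4/30 and 5/30 result does not depend on which of the three orderings is chosen, whereas the 3/30 result does.

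**What to change.** - In 13.1 and 13.5, reconcile the zero-response sentence with the more-than-2 continuation rule and the 65% figure, so that one stage 1 rule is stated.
- In 13.4, replace the fixed-sample interval with a prespecified two-stage exact 90% interval for each arm. Name the ordering (stagewise, Jennison-Turnbull) and compute it from the reconciled rule and the actual stage sizes.
- Keep the raw proportion as the reported point estimate. If the UMVUE is added, make it a supplement and state that it is unbiased only over all outcomes and exceeds the raw proportion in continuing arms (at a true 14%, mean 24.0% against 19.0%).

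The cost is a sentence or two of text and a few lines of code. The downside is a less familiar interval, with a higher upper limit at 3 to 7 of 30. It should be fixed before data are seen, because switching methods after a 5/30 result would look selective.

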2.6.2 Clinical Data

Tumor-treating fields (TTFields) are approved for use in patients with glioblastomas at recurrence (2011) or adjuvant setting (2016) due to overall survival benefit in various trials. In the EF11 study for recurrent glioblastoma, TTFields monotherapy showed a response rate of 14% compared to <5% response for any salvage therapy as per physician preference, including CCNU, bevacizumab, etc. (Stupp et al, Eur J Cancer 2012). The phase III (EF-14) trial for newly diagnosed glioblastoma also revealed an increase in median survival from 19.8 to 24.5 months for patients treated with adjuvant TTFields and temozolomide versus temozolomide alone.

Given preliminary preclinical data demonstrating synergy between TTFields and checkpoint immunotherapy, the rates and outcomes of combination TTFields and immunotherapy were analyzed in a retrospective gliomas cohort (Odia et al, Posters: SNO 2016 and AACR 2017; Schulte et al, SNO 2017).

Since 12/2012, 52 patients with newly diagnosed or recurrent gliomas were treated with TTFields therapy at Columbia University. Of 52 treated patients, 21 (40%) were women and 3 (6%), 5 (10%) and 43 (84%) had WHO grade II, III and IV gliomas, respectively. Median age at diagnosis was 58 (23-84) years. TTFields therapy was used at recurrence in 42 (81%), with a range of 0-4 prior recurrences. Prior therapies included bevacizumab (21, 20%), resection [gross total in 28 (54%)], radiation [mainly 60 Gy in 30 fractions, 44 (85%)] and temozolomide (100%). Median duration of TTFields therapy was 2.4 (0.1-20.3) months. Eleven (21%) patients met the TTFields compliance goal of 75%. Concurrent systemic therapy was used in 40 (77%), including

temozolomide (16, 31%), nitrosourea (4, 8%), bevacizumab (19, 37%), or checkpoint immunotherapy (28, 54%). Nivolumab was the predominant immunotherapy used and dosed 240 mg every 2 weeks. Only 2 (4%) experienced skin toxicity requiring TTFields therapy interruption.

Progression free (PFS) and overall (OS) survival among all patients was 3.6 and 21.5 months, respectively. Median PFS was significantly increased among glioblastoma patients treated with concurrent immunotherapy (4.6 vs. 3.5 months, p=0.04). There was a trend toward increased overall survival after TTFields therapy with addition of immunotherapy (8.3 vs. 6.5 months, p=0.32).

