5. TREATMENT PLAN

5.1 Study Design

This is an open-label Phase II trial with two parallel arms, two-stage design with appropriate stopping rules for poor efficacy. Arm A will enroll patients without prior history of any PD1/PDL1 checkpoint inhibitor, while Arm B will enroll patients with prior PD1/PDL1 checkpoint inhibitor. We expect to enroll at least 30 (15 in each Arm) and a maximum of 60 (30 in each Arm) evaluable subjects on this study. The study schema is depicted below.

NovoTTF200A (Optune) is a device to be worn continuously for a goal of \geq 75% of the time, ranging from 18 hours daily nonstop or 22 hours daily with 2-3 days off monthly. Patients will be encouraged to meet compliance goals via timely feedback and troubleshooting concerns. TTFields therapy begins once approved by insurance and an in-home initiation visit scheduled. The goal is to start within 1 month of starting immunotherapy infusions. Treatment is planned for ~24 months.

Infusions will start within 14 days of sreening/baseline visits. Nivolumab will be dosed every 2 weeks IV 240 mg as monotherapy and 3 mg/kg with ipilimumab. Nivolumab will not exceed 48 doses (24 months). Ipilimumab starts with the second infusion of nivolumab for Arm B (prior immunotherapy) or after progression on single agent nivolumab for Arm A (no prior immunotherapy). Ipilimumab infusions will be dosed as 1 mg/kg once every 6 weeks for a maximum of 4 doses (24 weeks).

Infusions will continue until maximum duration of ipilimumab and nivolumab therapy or when there is confirmed tumor progression, death, intolerable adverse effects or withdrawal. After the maximum of 24 months of therapy, clinical, radiographic and quality of life assessments are performed every 8 weeks until or when there is confirmed tumor progression, death, or withdrawal. One treatment cycle is defined as 6 weeks for the initial 24 months, thereafter every 8 weeks will define observation cycles.

Reported adverse events and potential risks are described in Section 7. Dose modifications are described in Section 6. No investigational or commercial agents or therapies other than those described below may be administered with the intent to treat the participant's malignancy.

5.2 **Pre-Treatment Criteria**

All patients must sign an informed consent prior to any study-specific procedure. For screening, patients will have the following tests done at the treating institution or in a local lab within 14 days of treatment initiation:

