5.4 End of Treatment Visit

For patients who come off study for toxicity or withdrawal of consent, tumor imaging is at the judgment of the investigator, suggested every 8-12 weeks in the appropriate setting after termination of the study therapy.

If patients come off treatment for progression of disease (Arm B only), intolerance, or withdrawal, they will be seen for assessments of efficacy and safety.

Patients will have repeat safety labs, a clinical examination, weight and KPS assessments, and concurrent medications within 30 days of the last infusion.

If tumor assessments are not done within 4 weeks, these will be obtained within the next 2 weeks after the End of Treatment Visit. After the end of treatment, each subject will be followed for 30 days for adverse event monitoring and 100 days for serious adverse event reporting. Participants removed from protocol therapy for unacceptable adverse events (Section 7) will be followed until resolution or stabilization of the adverse event.

Subjects who discontinue for reasons other than progressive disease will have post-treatment

follow-up for disease status until disease progression, initiating a non-study cancer treatment, withdrawing consent or becoming lost to follow-up. Subjects will be followed for survival every 2-3 months for a minimum of 1 year, or indefinitely until death or loss to follow-up.

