6. DOSING DELAYS/DOSE MODIFICATIONS

The descriptions and grading scales found in the revised NCI Common Terminology Criteria for Adverse Events (CTCAE) version 4.0 will be utilized for dose delays and dose modifications for nivolumab and ipilimumab.

Patients with Grade 3-4 scalp skin toxicity from NovoTTF200A (OptuneTM) application, should hold TTFields therapy until resolved to Grade ≤ 2 , then resume at same compliance goal of 75% or above. Interval maximal topical or systemic therapy advised. Repositioning of arrays is advised for any Grade ≤ 2 along with maximal medical therapy.

Adverse events (both non-serious and serious) associated with nivolumab and/or ipilimumab exposure may represent an immunologic etiology. These adverse events may occur shortly after the first dose or several months after the last dose of treatment. Immunotherapy must be withheld for drug-related toxicities and severe or life threatening toxicities. See Section 5.5.1 for supportive care guidelines, including use of corticosteroids.

Criteria for disrupting treatment, dose modification, or discontinuation for adverse events that are attributable to nivolumab or ipilimumab are listed below. After dose modifications are per the clinical judgment of the investigator and agreement of the subject, the treatment will be resumed according to the table below. Dose modification may not be required for adverse events that are clinically manageable.

Toxicity	Hold For Grade	Timing for Restarting Treatment	Treatment Discontinuation
Diarrhea/ Colitis	2-3	Toxicity resolves to Grade 0-1	Toxicity does not resolve within 12 weeks of last dose or inability to reduce corticosteroid to 10 mg or less of prednisone or equivalent per day within 12 weeks
	4	Permanently discontinue	Permanently discontinue
AST, ALT, or	2	Toxicity resolves to Grade 0-1	Toxicity does not resolve within 12 weeks of last dose
High Bili ru bin	3-4	Permanently discontinue (see exception below)	Permanently discontinue
Type 1 diabetes mellitus (new onset) or Hyperglycemia	T1DM or 3-4	Hold immunotherapy for new onset Type 1 diabetes mellitus or Grade 3-4 hyperglycemia associated with evidence of beta cell failure	Resume immunotherapy when patients are clinically and metabolically stable

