13.2 Definitions

Evaluable: All study-eligible patients who receive at least one infusion of nivolumab will be considered *evaluable for safety and toxicity*. To be *evaluable for efficacy*, patients must be study eligible, receive at least one cycle (6 weeks) of immunotherapy and complete initial disease assessment at ≥ 6 weeks after starting therapy.

Exclusions: Any patient who is enrolled on study, but does not receive any component of study treatment, will be excluded from all efficacy analyses. Any patient who initiates treatment and is later found to be ineligible for study (e.g., protocol violation) will be withdrawn from study but will be followed for disease progression, toxicity and survival. The experience of such patients will be characterized separately from that of evaluable patients. Reasons for exclusion of enrolled patients from the analysis set for efficacy, or for safety, will be characterized.

Overall response rate (ORR): Overall response rate is the proportion of patients whose best overall response per modified iRANO criteria or standard RANO criteria is complete (CR) or partial (PR) after at least 6 weeks from start of therapy. iRANO additionally requires best overall response of CR or PR to be sustained, that is, confirmed by a second assessment at \geq 4 weeks later. Patients who clinically progress before the initial radiographic assessment after 1 cycle (6 weeks) will be considered nonresponders.

Progression-free survival (PFS): PFS will be measured from the start date of treatment until

documented evidence of disease progression, clinical progression or death from any cause, after at least 8 weeks from start of therapy. Radiographic progression should be confirmed by a second assessment at \geq 4 weeks later. For patients who remain alive without progression, follow up time will be censored at the date of last assessment.

Overall survival (OS): Survival will be measured from the start date of treatment to the date of death from any cause or last contact (censored observations).

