APPENDIX D

TTFields Compliance Reports Generated by NovoTTF200A (OptuneTM)

Panels show example graphs of compliance: Top = Low compliance; Middle = Compliance near goal; Bottom = Compliance above goal of 75%. The report also includes the number of days included, which allows calculation of weighted averages across the duration of TTFields therapy.

APPENDIX E Toxicity Management Algorithms for Nivolumab (Appendix 3 of Investigator Brochure BMS-936558/MDX1106/ONO-4538)

Investigator Brochure BMS-936558/MDX1106/ONO-4538

nivolumab

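### If TTFields compliance is averaged over the whole device course, its exploratory association with PFS, OS and ORR is biased whenever wear changes over time

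*Combined protocol and SAP*

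**What the plan says.** Section 13.4 has device compliance collected at monthly home visits and averaged over each month. It then plans the outcome analysis in one sentence: "The weighted average will be compared to ORR, OS and PFS using the appropriate logistic or Cox regression models". Which average enters the model is not stated. Appendix D adds that each report gives its number of days, "which allows calculation of weighted averages across the duration of TTFields therapy".

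Section 13.2 starts both clocks at the beginning of treatment. For OS: "Survival will be measured from the start date of treatment to the date of death from any cause or last contact". PFS has the same origin, and the definition refers to events after at least 8 weeks. For ORR, "Patients who clinically progress before the initial radiographic assessment after 1 cycle (6 weeks) will be considered nonresponders". Section 5.1 aims for device start within a month of the first infusion, subject to insurance approval. No section gives a landmark, a lag, a fixed exposure window or a time-dependent covariate for compliance.

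Section 13.1 classes these correlations as exploratory. Reporting compliance against the 75% goal is a separate, descriptive objective (section 1.3).

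**The concern.** A course average is known only once the device course has ended, and progression is one of the things that ends it (section 5.8). A Cox model that carries this value from time zero uses the future to explain the present. The averaging window is short in patients who progress early and long in those who do well, so any change in wear enters the average with a weight that depends on the outcome.

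In Arm A the window may even run past the PFS event. Section 5.4 reads "If patients come off treatment for progression of disease (Arm B only", whereas section 5.8 makes no distinction between arms. Those two passages need to be reconciled.

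The risk is that an association produced by how long patients stayed well is read as a dose-response for the device.

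**Working it through.** The plan gives no effect size, power or significance level for this analysis, so there is no figure to reproduce.

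**Mechanism.** Let a patient wear the device for L months with wear w(u), in percentage points, u months after device start. The course average is X = (1/L) × the integral of w(u) from 0 to L.

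- Constant wear b: X = b for every L, so there is no bias.
- Linear change of c points a month: X = b + cL/2. Section 2.6.2 reports "Median duration of TTFields therapy was 2.4 (0.1-20.3) months". With c = −2, X falls by 2 × 2.4/2 = 2.4 points on the median course and by 2 × 20.3/2 = 20.3 points on the longest.
- A change of d points in one month only: X moves by d/L. One month is 1/2.4 = 42% of the median course and 1/20.3 = 5% of the longest, so a 20-point change moves X by 8.3 or 1.0 points.

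A drop just before progression therefore lowers X most in short courses, and high wear looks protective. A steady loss lowers X most in long courses, and high wear looks harmful.

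**Simulation with no effect of wear.**

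*From the documents:* median PFS 4.6 and OS 8.3 months (section 2.6.2); device start uniform over 0–1 month and a 24-month cap (5.1); censoring uniform over 12–36 months (from 13.3); n = 30 or 60.

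*Assumed:* exponential times, with PFS starting after a 6-week minimum; wear mean 63, SD 15, monthly noise SD 5. The mean gives P(wear > 75) = P(Z > (75 − 63)/15 = 0.8) = 21%, matching the 11 of 52 patients who met the goal in section 2.6.2. The device runs to progression, or stops earlier for outcome-independent reasons so that the median course is 2.4 months.

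Ratios are per 10 points. Rejection at 5% is only a yardstick.

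| Wear pattern | PFS HR | Rejection n=30 | Rejection n=60 |
|---|---|---|---|
| Stable | 1.00 | 5–6% | 5–6% |
| Fall of 10–30 points in last 1–2 months before progression | 0.92–0.72 | 10–79% | 16–97% |
| Loss of 2 points a month, device to progression | about 1.20 | 31% | 55% |
| Same loss, 2.4-month median course | 1.06 | 7% | 12% |

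- A rise of 2–5 points a month for 3 months gives PFS HR 0.97–0.87, with 6–33% rejection.
- With the 8-week PFS rule of section 13.2, the falls give about 0.94–0.73 and the steady loss (device to progression) 1.17. Rejection for the mildest fall at n=60 drops from 16% to 8%.
- Under the same falls, OS HR is 0.95–0.80. The ORR odds ratio is 1.09–1.77, using response rates of 14% and 35% and the response timing in section 2.4.3. These OS and ORR fall figures come from one model only.
- A second model with linear trends (starting wear mean 70, SD 15; n=60) gives PFS HR 1.26, 0.99 and 0.78 for −2, 0 and +2 points a month.

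**Landmark at week 12.** Twelve weeks is 2.76 months. The share with a PFS event by then is 1 − 2^(−(2.76 − m)/(4.6 − m)), where m is the minimum PFS time:

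- m = 0: 34%
- m = 1.38 months (6 weeks): 26%
- m = 1.84 months (8 weeks): 21%

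With first-report wear and time counted from week 12, the null PFS HR is 0.99–1.01 and rejection 4–8%, except 12–18% under the most severe fall.

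For ORR the gain is small. With uniform device start, a one-month first report ends after the 6-week scan (1.38 months) in 62% of patients. Rejection under the falls is still 6–49% (n=30) and 6–78% (n=60), against 6–65% and 7–92% with the course average.

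**The case against.** The nearest antecedent of the weighted average in section 13.4 is a per-month value, and the plan asks for appropriate models. A single early month, or a monthly time-dependent value, is not excluded and would largely avoid the problem. Appendix D says what the reports allow, not what enters the model. This stands: a reader might infer that the plan prescribes the course average, but the documents only make it the natural reading.

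A reader might also infer that the plan expects wear to change, so that bias is certain. The support is thin. Section 5.1 says "Patients will be encouraged to meet compliance goals via timely feedback and troubleshooting concerns", and section 6 says patients with Grade 3–4 scalp toxicity "should hold TTFields therapy until resolved to Grade" 2 or lower and then resume at the same goal. These make change possible, with no size, timing or direction. Section 2.6.2 reports only 2 of 52 patients (4%) with skin toxicity requiring interruption, and section 2.2.3 says dermatitis did not require substantial breaks. No passage describes wear falling before progression, which produces the largest figures. If only half of patients lose 10 points in the last month, the PFS HR is 0.95–0.97 and rejection 6–9%.

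Finally, this is an exploratory correlation in 30–60 patients with no decision attached, and a landmark discards later wear. That limits the weight of the point. It does not remove it, because a reader of the result could not tell a device effect from an artefact that can run in either direction.

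**Conclusion.** The point holds conditionally. If the course average is the covariate, the plan conditions on wear recorded after the time origin, over a window whose length depends on the outcome. The association is biased if wear changes and unbiased if it is stable.

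The size cannot be predicted from the documents. Over the assumed patterns and both PFS minimum-time rules, the null PFS HR per 10 points runs from about 0.72 to about 1.2, and the direction depends on the pattern. These figures rest on assumed wear trajectories, exponential times and retrospective medians from a mixed glioma cohort.

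It would be wrong to extend this to the primary ORR decision, the futility rule or the descriptive compliance objective. None of them uses this covariate. The change is worth making because it is cheap, and its priority is moderate.

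**What to change.** In section 13.4:

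- **PFS and OS:** do not enter the course average as a fixed covariate. Use compliance from the first monthly report that ends on or before week 12, and count time from week 12 in patients alive and progression-free then. A time-dependent covariate using only reports completed before each event time is an acceptable alternative or sensitivity analysis, although wear that falls because the patient is already worsening would still affect it.
- **Numbers:** report how many patients have no such report and how many leave before week 12. A 28–31-day report must begin by about week 7.6 to 8 (12 − 31/7 to 12 − 28/7), and the one-month device start is only a goal.
- **ORR:** show first-report compliance by response descriptively, or give an odds ratio with confidence interval and no p-value. Do not apply the week-12 restriction, so that early progressors stay in as nonresponders. State that bias is only partly reduced and that the report can overlap the first scan.
- **Reporting:** keep the course average as a descriptive summary and describe every result as an association.

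**Cost.** Wording and a little programming; the monthly reports are already collected. About 21–34% of patients leave the PFS and OS models (about 21% under the 8-week rule), and the landmark model ignores later wear. With stable wear and a true HR of 0.8 per 10 points, simulated PFS power falls from 67% to 49% at n=60 and from 37% to 24% at n=30. Some bias remains if wear has already fallen by the first report: up to about 12–18% rejection for PFS under the most severe fall.
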